### 3.3 Study Population

All refractive surgery candidates attending the above hospital for the purpose of phakic introcular lens implantation were included in the study. However, the initial group allocation occurred before the commencement of the study on the basis of surgeon and patient preference, thereby, randomization was on convenient basis.

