### 4.1 Sample size and statistical power

This study involves a convenient non-probability sample based on the availability of patients records in the respective center for enrolment and analysis.

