### 4.2 Statistical methods

After collection of data from patients records and its subjection to thorough analysis for incompleteness and exclusion criteria, these data will be stored electronically in sheet formats for later analysis. All statistical test and subsequent analyses will be performed using SPSS version 26 (IBM statistical software). Data will be classified into categorical and numerical. Categorical variables were described using frequencies and percentages and were analysed using Chi-squared test. Numerical variables, described as mean  $\pm$  standard deviation, will be subjected to tests of normality to determine the appropriate statistical tests for inter- and intra-group comparisons. Unpaired t test or Mann-Whitney test was used to compare the two groups (traditional and modified OVD) according to fulfilled statistical assumptions. These two groups were compared for statistically significant difference regarding all parameters that were collected as per section 3.5 of this protocol. These statistical comparisons were made both preoperatively to determine baseline characteristics of the study participants and postoperatively to determine any significant difference between the two groups. Within the same group whether traditional or reduced OVD, all of the aforementioned parameters were compared again pre- and postoperatively this time using either one sample paired t test or Wilcoxon signed-rank test according to fulfilled statistical assumptions. Significance was considered at P value less than 0.05.

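### Baseline differences between preference-formed groups are assessed only by P<0.05 tests whose result depends on an unplanned sample size, so non-significance cannot show comparability, and no adjustment is planned

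*Combined protocol and SAP*

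**What the plan says.** Section 3.3 states that "the initial group allocation occurred before the commencement of the study on the basis of surgeon and patient preference", so the groups are not randomised. Section 4.1 describes a "convenient non-probability sample based on the availability of patients records" and gives no target number.

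For the between-group analysis, section 4.2 says "These two groups were compared for statistically significant difference regarding all parameters that were collected" under section 3.5. The preoperative round of these tests is made "preoperatively to determine baseline characteristics of the study participants". For numerical variables, "Unpaired t test or Mann-Whitney test was used to compare the two groups", depending on assumptions. For the rest, "Categorical variables were described using frequencies and percentages and were analysed using Chi-squared test". The threshold is common to all: "Significance was considered at P value less than 0.05".

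Section 4.2 also describes numerical variables by mean and standard deviation. It plans no standardised difference, imbalance threshold, regression adjustment, matching or propensity method.

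**The concern.** When surgeon and patient choose the technique, the groups may differ in age, refraction, endothelial cell density or other features before surgery. The harm done by such a difference depends on its size in this sample and on how strongly the variable is related to the outcome. A significance test measures neither. It asks whether the difference exceeds what chance would produce at the sample size obtained.

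The same observed imbalance can therefore be non-significant in one sample and significant in a larger one. A baseline table of P values above 0.05 could be taken as support for attributing a postoperative difference, or the lack of one, to the OVD technique. If covariates were later chosen by baseline P value, the fault would carry into the adjusted analysis as well.

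**Working it through.** The plan gives no sample size, power or effect size, so there is no figure to reproduce.

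**Inputs from the documents.** Threshold 0.05 (section 4.2); unpaired t test for numerical variables (section 4.2).

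**Assumptions.** Two-sided tests, equal groups, independent observations, n per group from 20 to 200, and a true imbalance d of 0.3 or 0.5 SD.

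**1. Chance that a true imbalance is non-significant.** The t statistic follows a noncentral t distribution with 2n−2 degrees of freedom and noncentrality d/√(2/n). The miss probability is the chance that |t| falls below the 0.975 quantile of t. Example for d = 0.3, n = 30: noncentrality 0.3/0.258 = 1.16, critical value 2.00, miss probability 0.79.

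| n per group | d = 0.3 | d = 0.5 |
|---|---|---|
| 20 | 85% | 66% |
| 30 | 79% | 52% |
| 50 | 68% | 30% |
| 100 | 44% | 6% |
| 200 | 15% | 0.1% |

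The miss probability exceeds one half only below about 86 per group for 0.3 SD and about 32 for 0.5 SD. A categorical imbalance of 50% against 65% behaves much like 0.3 SD: missed 67% of the time at 50 per group, 43% at 100 and 14% at 200.

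**2. Smallest observed imbalance that reaches P<0.05.** This is t(0.975, 2n−2) × √(2/n).

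- n = 30: 2.002 × 0.258 = 0.52 SD
- n = 50: 1.984 × 0.200 = 0.40 SD
- n = 100: 1.972 × 0.141 = 0.28 SD
- n = 200: 1.966 × 0.100 = 0.20 SD
- n = 1,000: 1.961 × 0.0447 = 0.09 SD

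An observed difference of 0.30 SD is thus non-significant at 30 or 50 per group and significant at 100 or 200.

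**3. Bias left after a passed baseline test.** Take a true imbalance of 0.3 SD, a correlation of 0.6 with the outcome and no OVD effect. The unadjusted outcome difference is biased by 0.3 × 0.6 = 0.18 SD on average. In simulation (20,000 replicates), studies with a non-significant baseline test still carry about 0.12, 0.12 and 0.10 SD at 30, 50 and 100 per group. After linear adjustment for the baseline variable the bias is about zero at each size.

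**4. Behaviour of a 0.1 flag on the standardised difference.** With no true imbalance its standard error is about √(2/n), so the chance of exceeding 0.1 in absolute value is 2 × [1 − Φ(0.1/√(2/n))]: 70% at n = 30, 62% at n = 50 and 48% at n = 100.

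**The case against.** - **The plan never says that non-significance means comparability.** This stands. The stated purpose is only to determine baseline characteristics. A reader might infer that the groups will be declared alike, but no such rule is written, and section 3.3 is open about how the groups arose.
- **The sample may not be small.** This also stands. Section 3.4 screens all records without a limit on surgery date, although section 3.7 then removes anyone with a missing item. A reader might infer that a sizeable imbalance will usually go undetected. At 100 per group, however, a 0.5 SD imbalance is missed only 6% of the time, and at 200 a 0.3 SD imbalance only 15%.
- **Means, standard deviations and percentages are reported anyway.** This partly stands. If they are tabulated by group, which section 4.2 does not state, a reader can work out the standardised difference. The plan itself still judges the groups only by tests.
- **The bias comes from unadjusted outcome comparisons, not from the P values.** This stands and shapes the remedy. A column of standardised differences removes none of the bias in step 3; adjustment does.
- **A 0.1 flag also depends on sample size.** This stands, as step 4 shows, so the flag cannot serve as a pass/fail rule.

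**Conclusion.** The concern holds in a limited form. The planned between-group baseline assessment rests on P<0.05 tests whose result depends on a sample size that is neither planned nor stated. Non-significance therefore cannot show that these preference-formed groups are comparable, and significance in a large sample need not mean that a difference matters. No adjustment is planned to make up for this.

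The size of the problem is conditional on n: a 0.3 SD imbalance is missed in anything from 79% of studies at 30 per group to 15% at 200. These figures assume equal groups, two-sided tests and independent observations. Laterality is collected but the unit of analysis is not stated; if both eyes of a patient are counted, the percentages change. The documents support neither the claim that imbalances will usually be missed nor the claim that the groups will be called alike. This is an inexpensive improvement to the analysis plan and does not by itself invalidate the study.

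**What to change.** In section 4.2:

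1. Replace the preoperative significance tests with the standardised difference and its 95% confidence interval for each preoperative section 3.5 parameter: mean difference over pooled SD, or the equivalent for proportions, tabulated by group.
2. If values above 0.1 are flagged, use the flag for disclosure only, not as a pass/fail rule.
3. State that baseline P values will not be used to judge comparability or to choose covariates.
4. Name in advance the prognostic baseline variables already collected, for example age, preoperative refraction and the preoperative value of each outcome. Adjust the postoperative between-group comparison for them, by regression or a propensity method, whatever the baseline P values.

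The cost is revised wording, changed table columns and one adjusted model per outcome. No new data are needed. The downside is that the baseline table will look less favourable, and in small groups many parameters will exceed 0.1 by chance; the confidence intervals make that visible.

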## 2 Aim(s) / Objective (s)

Is omitting dispersive viscoelastic from the standard surgical technique and utilizing only cohesive OVDs (in what we call it reduced- OVD technique) safe and suitable?

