## **3.5 Study Interventions / Procedures**

After enrolment, the record of each participant is examined meticulously for completeness of preoperative and postoperative data pertaining to study including:

Patient age and gender, date of the procedure and its operative notes including laterality and surgical steps.

preoperative and postoperative assessments such as uncorrected and best corrected visual acuity, refractive error quantification both objectively utilizing an autorefractometer autorefractor Nidek ARK 1 (Nidek Inc, Gamagori, Japan) and subjectively as manifest refraction, clinical slit-lamp examination notes, intraocular pressure with air puff tonometers, AC depth assessment by Pentacam Scheimpflug (Oculus Optikgeräte GmbH Inc., Wetzlar, Germany), specular microscopy study of corneal endothelial cells (endothelial cell density (ECD), coefficient of variation (CV) and hexagonality) using Topcon SP-1p Specular Microscope (Topcon Corporation, Tokyo, Japan),

Typically, there is a preoperative visit and multiple postoperative visits extending over the period of 1-2 years after the procedure.

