## 2- Reduced OVD group

In this group of patients, the ICL was implanted with the use of cohesive OVD only.

There is one primary outcome of interest which is the unaided visual acuity after the surgery, and several secondary outcomes including postoperative intraocular pressure, corneal specular microscopy parameters (ECD, CV and hexagonality), and the observed adverse events that can happen during the operation or postoperatively.

Data will then be stored electronically in a sheet format to enable for later statistical analysis.

Data collection was started at the conduct of the study in March 2024, and it is expected to be completed 3-4 months later.

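### The aim is a safety question, but section 4.2 plans no confidence interval for the between-group difference, so a non-significant result would not show how much harm remains possible

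*Combined protocol and SAP*

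**What the plan says.** The aim in section 2 is a question: is leaving out the dispersive agent and "utilizing only cohesive OVDs (in what we call it reduced- OVD technique) safe and suitable"? Section 3.6 names the outcomes. It says "There is one primary outcome of interest which is the unaided visual acuity after the surgery". The secondary outcomes are IOP, the endothelial measures (ECD, CV, hexagonality) and "the observed adverse events that can happen during the operation or postoperatively".

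Section 4.2 sets out the between-group comparison. Numerical variables are summarised by mean and SD and tested by unpaired t or Mann-Whitney; categorical variables are summarised by frequencies and percentages and tested by Chi-squared. The purpose is stated in one sentence, "These two groups were compared for statistically significant difference regarding all parameters that were collected as per section 3.5 of this protocol", and repeated for the follow-up data: "postoperatively to determine any significant difference between the two groups". The threshold is P<0.05; sidedness is not given. The same section plans pre- versus postoperative tests within each group, by paired t or Wilcoxon signed-rank.

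Section 4.1, headed sample size and statistical power, gives neither: "This study involves a convenient non-probability sample based on the availability of patients records". Section 3.3 says that group membership followed surgeon and patient preference. No section mentions a confidence interval, a margin, or an allowance for two eyes from one patient.

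**The concern.** Whether a technique is safe is a question about how much harm can be ruled out. A test for a difference does not answer it. When the test is non-significant, the true difference may be negligible, or the sample may have been too small to show a difference that matters. The P value alone cannot tell these apart; an interval for the difference can.

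Three features of this plan sharpen the point. The sample is whatever the records yield, reduced further because section 3.7 excludes any participant with a missing item. The outcomes closest to safety are secondary. And section 6 suggests that the results might support work on reducing OVD further, so unwarranted reassurance could carry forward.

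**Working it through.** The plan states no sample size, power, SD, effect or event rate, so it has no figure to reproduce. Everything below is illustrative. Assumed: equal groups of n, two-sided 5% level, normal data with a common SD, and, except in step 5, independent eyes.

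**1. Precision that the plan would leave unreported.** The half-width of the 95% CI for a mean difference, in SD units, is t(0.975, 2n−2) × √(2/n).

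**2. Chance of a non-significant result when there is a real deficit.** For a true deficit of 0.4 SD (assumed), the t statistic is noncentral t with 2n−2 degrees of freedom and noncentrality 0.4 × √(n/2). The chance is 1 minus the power.

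| n per group | CI half-width (SD) | Power at 0.4 SD | Non-significant |
|---|---|---|---|
| 30 | 0.52 | 0.332 | 67% |
| 50 | 0.40 | 0.508 | 49% |
| 100 | 0.28 | 0.804 | 20% |
| 200 | 0.20 | 0.979 | 2% |

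**3. The same P with different meanings.** Take P=0.30 at two sample sizes.
- n=30: observed difference 0.270 SD; 0.270 ± 0.517 gives −0.25 to +0.79 SD.
- n=200: observed difference 0.104 SD; 0.104 ± 0.197 gives −0.09 to +0.30 SD.

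Under section 4.2 both would be reported as no significant difference. The first is compatible with a large deficit; the second rules out anything beyond about 0.3 SD.

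**4. Adverse events.** With no events among n independent eyes, the exact two-sided 95% upper limit is 1 − 0.025^(1/n). At n=50 this is 7.1%, so zero observed events would still allow a true rate of about 7%. For 2/50 versus 0/50, the rate difference is 4 points and its Newcombe 95% CI is −3.7 to +13.5 points. Uncorrected Chi-squared gives P=0.15 and Fisher's exact test P=0.49. The expected number of events is only 1 per group, so the Chi-squared P is itself unreliable here. On either test the result is non-significant, and only the interval shows that an excess of 13 points has not been excluded.

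**5. If both eyes are entered.** Section 3.5 collects "date of the procedure and its operative notes including laterality and surgical steps", and no section says whether the unit of analysis is the eye or the patient. If 50 eyes per group were both eyes of 25 patients with between-eye correlation 0.5, all treated the same way, the half-width from patient means would be t(0.975, 48) × √((2/25) × (1+0.5)/2) = 0.49 SD, against 0.40 SD if pairing were ignored. Simulated coverage of the nominal 95% interval that ignores pairing is then about 89%.

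**The case against.** **The estimate is not really missing.** Means, SDs and percentages are planned for two defined groups, so the crude difference is one subtraction away, and with group sizes a reader could approximate an interval for t-tested outcomes and event rates. This stands, and the point is accordingly limited to the missing interval. Such a reconstruction would not serve skewed outcomes tested by Mann-Whitney, and would generally be too narrow if both eyes of a patient were in the same group.

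**Other safety evidence is planned.** The within-group pre/post tests cover IOP and the endothelial measures in the reduced-OVD group, and adverse events are an outcome. This narrows the criticism, but these analyses have no planned intervals either, and a within-group change does not bound the difference between techniques.

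**The plan never says that a non-significant result means safe.** Correct. A reader might infer such a rule from the pairing of a safety aim with difference tests, but the documents contain no decision rule for safety. The gap is in reporting precision; no wrong inference is written into the plan.

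**The numbers say nothing about this study.** Also correct. A reader might conclude that the study is too small. The documents do not support that: section 3.4 screens all records whatever the date of surgery, so the sample could be large or small.

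**Pairing is conjecture.** A reader might take it that eyes will be pooled as if independent. The text does not say so, and sections 3.6 and 3.7 speak of patients and participants throughout. The pairing point is conditional on both eyes being entered.

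**Conclusion.** The point holds in a limited form and should be fixed. The between-group analysis consists of difference tests with descriptive summaries, no interval for the difference is planned, and no sample size or power is given. A non-significant result would therefore leave the aim unanswered. The absence of a planned interval is certain from the text. Its practical size is unknown because it depends on the number of eyes or patients: for an assumed 0.4 SD deficit, the chance of missing it runs from 67% at 30 per group to 2% at 200 per group. In a large sample the consequence could be small. Even a narrow interval would describe an unadjusted comparison between groups formed by preference, so it would address imprecision but not confounding.

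**What to change.** Change section 4.2 as follows.

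1. For unaided visual acuity, IOP, ECD, CV and hexagonality, report the reduced-minus-traditional difference with its 95% CI, using the Hodges-Lehmann estimate and interval where Mann-Whitney is the test.
2. Report each adverse-event rate with an exact 95% CI, and the rate difference with a 95% CI (for example Newcombe).
3. If both eyes of a patient are included, compute the intervals with an allowance for clustering by patient. Averaging the two eyes is an option only when both had the same technique.
4. State that P>=0.05 alone will not be taken as evidence of safety, and that the safety conclusion will describe the largest harm that the interval still allows. Add the caveat that the comparison is unadjusted and that allocation followed surgeon and patient preference.

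If outcomes have already been analysed, set no margin and make no formal claim that the reduced technique is not worse; report the intervals as they are.

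The cost is modest. The data are the same and the analysis a little longer, though the Hodges-Lehmann, rate-difference or clustered intervals may need an extra procedure or another program. Some outcomes may look less reassuring than a non-significant P would have made them appear.

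### Section 4.2 never compares the two techniques using each eye's own baseline, so ECD, CV, hexagonality and IOP are compared less precisely than the collected data allow and without protection against baseline imbalance

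*Combined protocol and SAP*

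**What the plan says.** Section 4.2 sets out three sets of comparisons for numerical variables.

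- **Between groups, before and after surgery separately.** "Unpaired t test or Mann-Whitney test was used to compare the two groups (traditional and modified OVD) according to fulfilled statistical assumptions". The section applies these tests once to the preoperative values, to describe baseline, and once to the postoperative values, to look for a difference between the techniques.
- **Within each group.** "Within the same group whether traditional or reduced OVD, all of the aforementioned parameters were compared again pre- and postoperatively". Here the choice lies between a paired t test and its signed-rank counterpart, again depending on whether assumptions are met.
- **Threshold.** "Significance was considered at P value less than 0.05", with no statement of sidedness.

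The section names no change score compared between groups, no analysis of covariance and no group-by-time term. Section 3.6 lists IOP, ECD, CV and hexagonality among the secondary outcomes and does not define any of them as change from baseline. Section 3.5 requires their pre- and postoperative values, and section 3.7 excludes any participant with a missing item, so every analysed record should have a baseline. On allocation, section 3.3 says that "the initial group allocation occurred before the commencement of the study on the basis of surgeon and patient preference". Section 4.1 gives no sample size, power, effect size or SD.

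**The concern.** Section 2 asks whether leaving out the dispersive viscoelastic is safe. For the endothelium and for pressure, that becomes a contrast: do eyes lose more cells, or end with higher pressure, under one technique than under the other, given where they started? Section 4.2 splits this into pieces that do not meet. The between-group test ignores where each eye started. The within-group tests use the starting value but compare nothing between techniques.

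Three things are at stake.

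1. **Precision.** Eyes differ widely in ECD before surgery. Leaving that variation in the comparison widens the interval, and in a safety study low power favours a reassuring non-significant result.
2. **Baseline imbalance.** In groups formed by preference, a difference present before surgery reappears in the postoperative values and may imitate or hide an effect of technique.
3. **Reporting.** Two within-group P values printed side by side can be read as a comparison. Each depends on its own group's size and variability, and neither tests the difference.

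**Working it through.** The plan has no figure of its own to reproduce. All values below are assumptions: two-sided alpha 0.05, independent eyes, equal SD before and after surgery.

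**1. Precision of the between-group comparison.** Inputs: ECD level SD 300 cells/mm2, true extra loss 75, n = 100 eyes per group, pre-post correlation r varied.

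SE = S × √(2/n); power ≈ Φ(75/SE − 1.96), the opposite tail being negligible; 95% CI half-width = 1.96 × SE.

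- Postoperative values (as planned): S = 300, SE = 300 × √(2/100) = 42.4, 75/42.4 = 1.77, power 42%, half-width 83.
- Raw change: S = 300 × √(2(1 − r)).
- ANCOVA on baseline: S = 300 × √(1 − r²).

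| r | S, change | Power, change | S, ANCOVA | Power, ANCOVA | Half-width, ANCOVA |
|---|---|---|---|---|---|
| 0.3 | 355 | 32% | 286 | 46% | 79 |
| 0.5 | 300 | 42% | 260 | 53% | 72 |
| 0.7 | 232 | 63% | 214 | 70% | 59 |
| 0.8 | 190 | 80% | 180 | 84% | 50 |
| 0.875 | 150 | 94% | 145 | 95% | 40 |

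Raw change is worse than the planned test below r = 0.5 and equal to it at 0.5. ANCOVA is ahead throughout this range.

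**2. Baseline imbalance.** If one group starts B higher and loses E more, the expected postoperative difference is B − E.

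Simulation (10,000 datasets; SD 250, r = 0.8, 50 eyes per group, B = 75):

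- E = 0: the postoperative test is falsely significant in 31%; a between-group test of change in 5%.
- E = 75: the expected postoperative difference is 75 − 75 = 0. The postoperative test is significant in 5%, the change test in 66%. The preoperative test flags the imbalance in only 33%.

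ANCOVA was not simulated here. With equal SDs its slope is r, so it removes 0.8 × 75 = 60 of the imbalance and leaves 15.

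**3. Within-group P values when the techniques are identical.** Inputs: SD of change 150, same true loss L in both groups. The power p of each paired t test comes from the noncentral t with noncentrality (L/150) × √n. The chance that exactly one group is significant is p1(1 − p2) + p2(1 − p1).

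| Loss L | 40 vs 160 eyes | 50 vs 50 | 100 vs 100 |
|---|---|---|---|
| 25 | p = 0.177, 0.554: 53% | p = 0.211: 33% | p = 0.379: 47% |
| 50 | p = 0.538, 0.987: 46% | p = 0.637: 46% | p = 0.910: 16% |
| 75 | p = 0.869, >0.999: 13% | p = 0.934: 12% | p = 0.999: 0.3% |

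A valid between-group test would be significant in about 5% of such studies. Discordance is frequent when within-group power is moderate and rare when it is high. Unequal group sizes are not needed: at a loss of 50, 40 vs 160 and 50 vs 50 both give 46%.

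**The case against.** The strongest defence is that the plan does compare the techniques. It assigns that task to the between-group tests, which are run "postoperatively to determine any significant difference between the two groups". If the groups have equal baseline means, the expected difference in postoperative ECD equals the expected difference in change. The planned test then estimates the same quantity, unbiased and less precisely. This stands. A reader might infer that the plan lacks a between-group test, or that it tests the wrong quantity; section 4.2 supports neither. Bias enters only with baseline imbalance, which preference allocation makes plausible but which cannot be shown from the documents.

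A reader might also infer that the investigators will call the techniques different if only one group shows a significant fall. Section 4.2 says no such thing. The misreading is a foreseeable reporting risk: both sets of P values are planned for every parameter and nothing warns against it. Nor does the risk have a single size. With the assumptions in part 3 it runs from 53% down to 0.3%, driven largely by the assumed loss.

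Comparing raw change is a tempting repair, but it would lose power for any outcome with r below 0.5. The correlations for IOP, CV and hexagonality are unknown here.

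Finally, the outcomes affected are secondary, and the primary analysis of unaided acuity is untouched. That limits the weight of the point. It does not remove it, because these outcomes carry much of the safety question in section 2.

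**Conclusion.** The point holds as a gap in the use of available data, plus a reporting risk. No planned between-group analysis uses the eye's own baseline.

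Under the part 1 assumptions, baseline adjustment moves power from 42% to between 46% and 95%, and narrows the ECD interval from ±83 to between ±79 and ±40 cells/mm2. The gain is small if pre and post values correlate weakly and large if they correlate strongly. Baseline adjustment also removes most of a measured ECD imbalance when r is high, but not all of it, and it does nothing for unmeasured differences between patients who received each technique.

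The structural finding rests on the text of section 4.2 and is firm. The magnitudes rest on assumed SDs, correlations, losses and group sizes, and on independent eyes; the documents do not say whether eye or patient is the unit of analysis. The change should be made, but the primary outcome does not depend on it.

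**What to change.** Revise section 4.2 as follows.

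- For ECD, CV, hexagonality and IOP, make the planned between-group analysis an ANCOVA of the postoperative value at one named visit, on group and the eye's own preoperative value. Report the adjusted difference with its 95% CI.
- Name that visit. Sections 3.3 and 3.5 describe several postoperative visits over one to two years, and none is designated for analysis.
- If both eyes of a patient are entered, allow for the pairing in the model.
- Report within-group change as a mean with 95% CI, for description only, and state that within-group P values are not used to compare the techniques.
- Leave unaided visual acuity on its postoperative value, since its change mainly reflects the refractive error that was corrected.

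The cost is SAP wording, the choice of one analysis visit, and one model per outcome. The data are already required by section 3.5.

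### Postoperative unaided acuity is never referred to each eye's preoperative best-corrected acuity, and no count of eyes losing best-corrected lines is planned

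*Combined protocol and SAP*

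**What the plan says.** Section 3.6 (under the Reduced OVD group) sets the primary outcome: "There is one primary outcome of interest which is the unaided visual acuity after the surgery". It gives no scale, time point or reference value. The secondary outcomes are "several secondary outcomes including postoperative intraocular pressure, corneal specular microscopy parameters (ECD, CV and hexagonality") and observed adverse events, which are not defined. BCVA is not named there, although the list is open-ended.

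Section 3.5 collects "preoperative and postoperative assessments such as uncorrected and best corrected visual acuity", so both acuities should be available before and after surgery. Section 3.7 excludes any participant with a missing section 3.5 item.

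Section 4.2 applies two analyses to every section 3.5 parameter:

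- **Between groups**, before surgery to describe baseline and then "postoperatively to determine any significant difference between the two groups": "Unpaired t test or Mann-Whitney test was used to compare the two groups".
- **Within each group**, where "all of the aforementioned parameters were compared again pre- and postoperatively", "using either one sample paired t test or Wilcoxon signed-rank test according to fulfilled statistical assumptions".

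Numerical variables are summarised by mean and standard deviation. Nothing in the document relates postoperative UCVA to preoperative BCVA, and no category of BCVA lines lost or gained is defined.

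**The concern.** Three things follow from setting these sections side by side.

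1. Preoperative UCVA chiefly measures the refractive error that the lens is implanted to correct. A significant within-group gain is expected under either OVD technique, so its P value does not bear on the aim in section 2.

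2. The between-group comparison of postoperative UCVA does bear on the aim, but section 3.3 says that allocation followed surgeon and patient preference, and section 4.2 plans no adjustment. An eye's unaided result is limited by its best-corrected potential. The exclusion criteria remove retinal and corneal disease but do not name amblyopia. If the groups differ in preoperative BCVA, that difference enters the primary comparison directly.

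3. The aim is safety. A few eyes losing best-corrected lines could leave the group mean or rank distribution almost unchanged, and no tabulation is planned that would show them.

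At stake are a primary comparison that may reflect patient mix instead of technique, and visual harm in a minority of eyes that goes unreported.

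**Working it through.** The plan states no sample size, acuity scale, standard deviation or margin, so there is no figure of its own to reproduce. Every input below is an assumption chosen for illustration. On the logMAR scale lower is better, and two lines are 0.20. Tests are taken as two-sided at 0.05.

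**1. Within-group UCVA test.** Approximate power is Φ(gain × √n / SD − 1.96), where SD is the SD of change.

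| n | gain | SD | power |
|---|---|---|---|
| 20 | 0.3 | 0.4 | Φ(3.354 − 1.96) = 92% |
| 20 | 0.3 | 0.3 | Φ(4.472 − 1.96) = 99% |
| 20 | 1.0 | 0.4 | Φ(11.18 − 1.96) > 99.9% |
| 30 | 0.3 | 0.4 | Φ(4.108 − 1.96) = 98% |

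Significance is close to certain even for a modest correction.

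**2. Between-group UCVA comparison.** Suppose that the two techniques are identical but the groups differ in mean preoperative BCVA by d. Take the SD of BCVA as 0.10 and the residual SD of postoperative UCVA around it as 0.08.

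- SD of raw UCVA = √(0.10² + 0.08²) = 0.128.
- z = d / (0.128 × √(2/n)), with n per group. The chance of false significance is Φ(z − 1.96) + Φ(−z − 1.96).

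| d | n per group | z | false significance |
|---|---|---|---|
| 0.02 | 50 | 0.78 | 12% |
| 0.02 | 100 | 1.10 | 20% |
| 0.05 | 50 | 1.95 | 50% |
| 0.05 | 100 | 2.76 | 79% |

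Simulating the t test gives nearly the same rates (about 49% and 78% to 79% at d = 0.05). Postoperative UCVA minus preoperative BCVA does not contain d in this model, and its simulated rate is about 5% throughout.

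**3. Mean BCVA when a minority lose two lines.** If a fraction f lose 0.20 and the rest gain g, the mean change is 0.20f − (1 − f)g.

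| f | g | mean change |
|---|---|---|
| 5% | 0.05 | 0.010 − 0.0475 = −0.0375 (improves) |
| 10% | 0.05 | 0.020 − 0.045 = −0.025 (improves) |
| 10% | 0.02 | 0.020 − 0.018 = +0.002 (worsens) |
| 5% | 0 | +0.010 (worsens) |
| 10% | 0 | +0.020 (worsens) |

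The sign depends on g. At f = 5% the mean improves only if the other eyes gain more than 0.010 / 0.95 = 0.0105.

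With g = 0.05, added noise of SD 0.06 and n = 50, 3,000 simulated samples gave a significant improvement in 84% (paired t) and 97% (Wilcoxon) of runs at f = 5%, and in 46% and 79% at f = 10%. Rank tests do not reveal the losers.

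**4. Between-group BCVA.** An extra 5% of eyes losing two lines shifts the mean by 0.05 × 0.20 = 0.01. At SD 0.08 to 0.10, power is 7% to 9% with 50 per group and about 10% to 14% with 100. Reaching 80% would need 1,005 to 1,570 per group.

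**5. What a line-loss count can deliver.** Separating 1% from 5% needs 285 per group for 80% power. With no such eye observed, the one-sided 95% upper bound is 1 − 0.05^(1/n): 9.5% at n = 30, 5.8% at n = 50 and 3.0% at n = 100. The count therefore describes and bounds harm; it would rarely support a test.

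**The case against.** The strongest reply is that section 4.2 already contains the comparison that answers the study question. The primary outcome is a postoperative value, the two groups are compared on it, and the pre/post test is only additional. That stands. A reader might infer that the plan would declare any working lens a success whatever the technique, but the document defines no success criterion and does not treat a pre/post gain as evidence for the technique.

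A reader might also infer that BCVA is handled only as a mean. It is not: standard deviations are reported, rank tests are allowed, and BCVA is compared between groups as well as within them. Nor can one say that there is no visual safety endpoint. Adverse events are a secondary outcome and could include acuity loss, and the secondary list is open-ended. What remains is that acuity loss is named nowhere and that group-level tests, including rank tests, are weak for a small minority of eyes.

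The baseline comparison of BCVA could reveal an imbalance in visual potential. That is true, but nothing is planned to act on it, and a non-significant baseline test does not show balance.

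Finally, the magnitudes rest on chosen inputs, the two-line cut-off is the reviewer's and not the plan's, and line-loss events will be too few for a useful test. All three points are accepted. They argue for description with an interval, not for leaving the count out.

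**Conclusion.** The point holds as a limited but worthwhile improvement. The within-group UCVA test is uninformative about OVD technique. The between-group UCVA comparison is the relevant one, but it is exposed to any imbalance in best-corrected potential because allocation was by preference and no adjustment is planned. Under the assumed SDs, false significance is 12% to 20% for an imbalance of 0.02 logMAR and 50% to 79% for 0.05, with 50 to 100 eyes per group, against a nominal 5%. Whether such an imbalance exists cannot be known from the documents.

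Line loss in a minority of eyes could be missed, because the planned summaries and tests work at group level and no count is specified. Whether mean BCVA would actually improve in that case depends on the gain assumed in the other eyes, so masking by an improved mean is a possibility, not a prediction.

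**What to change.** In sections 3.6 and 4.2, state that acuities are analysed in logMAR, and then:

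- **(a) Primary comparison.** Compare postoperative UCVA between groups relative to each eye's preoperative BCVA, either as the difference or with preoperative BCVA as a covariate. Choose one and state it before the analysis. Keep pre/post UCVA as description without a P value.
- **(b) Visual safety.** Name change in BCVA (postoperative minus preoperative) as a safety outcome. Report by group the number and percentage of eyes losing two or more lines, with a confidence interval, as description and not as a test.

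Both should refer to a stated postoperative visit, since the plan names none for the primary outcome.

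The cost is a few sentences of SAP text and two derived columns. No new data are needed, because section 3.5 collects both acuities and section 3.7 removes participants lacking either. Adjustment for preoperative BCVA deals with that one source of imbalance only, and the line-loss intervals will be wide.
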